Human PET-CT Protocol: [¹¹C]MRB will be synthesized at the Yale PET center based on procedures described and previously performed ^{1,2}. An intravenous bolus dose of MRB (~20mCi) will be injected by an infusion pump. PET data will be acquired dynamically for 120 min using the Siemens mCT-X whole-body PET/CT scanner using continuous bed motion to image perform multiple PET bed acquisitions from the top of the head to the lower abdominal region. A CT scan will be performed for attenuation correction and to help delineate the BAT and other regions of interest (ROIs). Images will be reconstructed with an ordered subset expectation maximization algorithm using point spread function correction and time-of-flight information. To delineate fat (WAT, BAT) and skeletal muscle regions of interests (ROIs), CT images are first resliced to match the resolution and location of PET images. As performed in previous studies ², a supraclavicular ROI is first manually drawn on the CT images. Within that area, the fat ROI is segmented using the CT images and an intensity window from -200 to -50 HU. Subsequently the fat ROI is segmented into WAT and BAT ROIs by using the ¹¹C-MRB PET images: Standardized Uptake Value (SUV) \geq 1.25 for BAT, SUV $<$ 1.25 for WAT. Brain ROIs for predetermined NET-rich areas of the brain, including the locus ceruleus, raphe, thalamus and hypothalamus were defined in template space and are applied to the PET images by using the participant's MR image as an intermediate step. For analysis of tracer uptake, mean SUV will be reported for segmentation of adipose tissue. Because the distribution volume ratio (DVR) is a more precise measurement of uptake for reversible tracers ³ such as ¹¹C-MRB, regional quantification of ¹¹C-MRB uptake as DVR (V_T/V_{ND}), estimated via multilinear reference tissue model 2 (MRTM2) ^{4,5} ($t^*=30$ min) using the occipital cortex, a region with low NET density ^{2,5,6} as the reference region. MRTM2 reduces the variability of MRTM (4) parameter estimates by fixing one of the three parameters, the parameter k_2' , which is only related to the reference region time-activity curve, to a common value for all target regions. In this study, the parameter k_2' was fixed to 0.021 min⁻¹, based on previous brain studies and previous BAT PET studies ². In addition to DVR, MRTM2 can estimate R_1 , the relative radioligand delivery, using a 1 tissue compartment model (1TC). For

HIC 2000030749

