3.2.1 Potential Risks

Risks Associated with Radiation:

Yale University Radioactive Investigational Drug Committee (Yale RIDC) will review the use of radiation in this research study, and no subjects will be scanned until RIDC approval is obtained. This research study involves exposure to radiation from [¹¹C]MRB PET scanning. This radiation exposure is not necessary for medical care and is for research purposes only.

For each individual PET scan, subjects will receive up to \leq 20 mCi of, [¹¹C]MRB, plus transmission scans. This is equal to an effective dose of 0.428 rem per injection.

HIC 2000030749

Although each organ will receive a different dose, the maximum amount of radiation exposure subjects will receive from participating in up to two PET scans is equal to an effective dose 0.856 rem, for a total of up to 40 mCi of [¹¹C]MRB in 2 injections. This calculated value is used to relate the dose received by each organ to a single value.

Subjects will also receive radiation exposure from low dose whole-body CT scans on the mCT, subjects will receive up to 1250 mrem (1.250 rem) from up to 2 low dose head CT scans (0.625 rem each).

The maximum amount of radiation an individual subject could receive in this study is from up to 2 injections of \leq 20 mCi of [¹¹C]MRB, plus CT scans. This is equal to an ED of 2.106 rem.

The amount of radiation subjects will receive in this study is below the dose guidelines established by the RIDC guidelines for research subjects. This guideline sets an effective dose limit of 5 rem per year.

Adverse effects of the radiopharmaceuticals in this study have not been reported. However, the possibility exists for a rare reaction to any of the substances or procedures to which a subject is exposed.

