6.1.2 Dosage, Administration, Schedule

N/A

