Human PET-CT Protocol: [11C]MRB will be synthesized at the Yale PET center based on procedures described and previously performed 1,2. An intravenous bolus dose of MRB (~120mCi) will be injected by an infusion pump. PET data will be acquired dynamically for 120 min using the Siemens mCT-X whole-body PET/CT scanner using continuous bed motion to image perform multiple PET bed acquisitions from the top of the head to the lower abdominal region. A CT scan will be performed for attenuation correction and to help delineate the BAT and other regions of interest (ROIs). Images will be reconstructed with an ordered subset expectation maximization algorithm using point spread function correction and time-of-flight information. To delineate fat (WAT, BAT) and skeletal muscle regions of interests (ROIs), CT images are first resliced to match the resolution and location of PET images. As performed in previous studies 2, a supraclavicular ROI is first manually drawn on the CT images. Within that area, the fat ROI is segmented using the CT images and an intensity window from -200 to -50 HU. Subsequently the fat ROI is segmented into WAT and BAT ROIs by using the 11C-MRB PET images: Standardized Uptake Value (SUV) ≥ 1.25 for BAT, SUV < 1.25 for WAT.

Brain ROIs for predetermined NET-rich areas of the brain, including the locus ceruleus, raphe, thalamus and hypothalamus were defined in template space and are applied to the PET images by using the participant's MR image as an intermediate step. For analysis of tracer uptake, mean SUV will be reported for segmentation of adipose tissue. Because the distribution volume ratio (DVR) is a more precise measurement of uptake for reversible tracers 3 such as 11C-MRB, regional quantification of 11C-MRB uptake as DVR (VT/ VND), estimated via multilinear reference tissue model 2 (MRTM2) 4,5 ($t^*=30$ min) using the occipital cortex, a region with low NET density 2,5,6 as the reference region. MRTM2 reduces the variability of MRTM (4) parameter estimates by fixing one of the three parameters, the parameter $k2'$, which is only related to the reference region time-activity curve, to a common value for all target regions. In this study, the parameter $k2'$ was fixed to 0.021 min-1, based on previous brain studies and previous BAT PET studies 2. In addition to

HIC 2000030749

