DVR, MRTM2 can estimate R1, the relative radioligand delivery, using a 1 tissue compartment model (1TC). For the 1TC model, volume of distribution, $VT = K1/k2$, where $K1$ (mL/min-1/mL-1) is the rate constant of radiotracer from plasma to tissue of target organ and $k2$ is the rate constant from tissue to plasma. Using a reference region with non-displaceable binding (e.g. occipital lobe) we can estimate similar rate constants: $VND = K'1/k'2$. Recalling that $K1$ and $K'1$ are the rate constants for transfer from plasma to the tissue and reference region, respectively, then we can estimate relative radioligand delivery as $R1 = K1/K'1$.

Visit 3 – Whole body PET/CT Imaging Visit - High-Carbohydrate Mixed Meal Test (MMT)

High Carbohydrate Mixed meal test (MMT):

After 2 weeks from visit 2, participants will come to the PET Center after a 10-hour overnight fast. A nurse will insert an intravenous (IV) catheter and subjects will ingest a liquid meal (65% CHO, 20% fat, and 15% protein, equal to 40% of daily energy expenditure, per ~16 ounces) to be prepared by the Metabolic Kitchen located at the HRU. Blood samples will be collected at -10, 0, 15, 30, 60, 90, and 120 min for measurement of glucose, insulin and C-peptide concentrations 7. Plasma samples will be drawn at baseline and throughout the MMT for measurement of additional hormones (such as leptin, ghrelin, thyroid hormones, and catecholamines) and free fatty acids (FFA) levels. Insulin and glucose will be used to calculate indexes of insulin sensitivity 7-9. Hormones, glucose and FFA will be correlated with PET measurements of brown fat at baseline and during the MMT. Approximately 60 mL of blood will be drawn at this visit.

Participants will undergo whole body [11C]MRB PET scan as described in visit 3. After the MMT, PET data will be acquired dynamically for 120 min using the Siemens mCT-X whole-body PET/CT scanner after an intravenous bolus dose of MRB (~20mCi).

The order of the PET scan visits 2 and 3 will be randomized.

Measurement of Energy Intake: Hunger and fullness will be determined immediately before, during and after the PET scans with Visual Analog Scales (VAS).

Visit 4 – Sympathetic Nervous System Activity (SNSA) measurement Visit - Fasting

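### Sections 5.1 and 6.3 print about 120 mCi for the Visit 2 injection against a 20 mCi cap, and the protocol's two radiation totals do not reconcile

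*Combined protocol and SAP*

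**What the plan says.** **Injected activity.** The Visit 2 PET procedure appears three times. The synopsis reads "An intravenous bolus dose of MRB (~20mCi) will be injected by an infusion pump". Sections 5.1 and 6.3 carry the same sentence with a different number: "An intravenous bolus dose of MRB (~120mCi) will be injected by an infusion pump". Visit 3 is about 20 mCi in all three places; section 6.3, for example, has "scanner after an intravenous bolus dose of MRB (~20mCi". Section 3.2.1 limits each scan to 20 mCi and describes two injections "for a total of up to 40 mCi". Section 6.1.2, which should state the dose, is marked not applicable.

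**Radiation dose.** Section 3.2.1 gives the tracer dose at 20 mCi: "This is equal to an effective dose of 0.428 rem per injection". For CT it gives "up to 1250 mrem (1.250 rem) from up to 2 low dose head CT scans (0.625 rem each". Its overall ceiling begins "The maximum amount of radiation an individual subject could receive in this study is from up to 2 injections" and comes to 2.106 rem. The Radiation paragraph under Minimizing Risks in the same section also names DXA as a source. Section 6.2.3 instead describes up to three injections of 20 mCi, up to three CTs and DXA, and puts the total at about 2.307 rem, or 7.69 years of background.

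**Where the total is used.** Section 3.2.1 (Radiation) and exclusion 13 in 5.3.2 bar people whose past-year research exposure, together with this study, would pass the yearly limit. Section 5.1 allows two attempts at a failed or incomplete scan.

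**The concern.** The injected activity is a safety figure, and two of the three descriptions of the procedure give a value that the risk section rules out. Someone working from 5.1 or 6.3 finds no dosage section to correct it.

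The dose totals raise a different problem. Sections 3.2.1 and 6.2.3 describe the same study with different scan counts, and their totals do not scale with those counts: half as many scans again, plus DXA, adds only 0.201 rem. The prior-exposure exclusion cannot be applied consistently until one total is fixed. Ethics and radiation committees, and participants, also need one correct exposure figure.

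**Working it through.** **Inputs.** Visit 2 activity: about 120 mCi (5.1, 6.3) or about 20 mCi (synopsis). Visit 3: about 20 mCi. Cap: 20 mCi per scan, 40 mCi in total (3.2.1). Unit doses from 3.2.1: 0.428 rem per injection and 0.625 rem per CT. Stated totals: 2.106 rem (3.2.1) and 2.307 rem (6.2.3). DXA: no rem value; 3.2.1 puts it at one tenth of a chest X-ray. Guideline limit: 5 rem per year (3.2.1, 6.2.3).

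**Activity**
- 120 / 20 = 6 times the per-scan cap.
- Visits 2 and 3 as printed in 5.1 and 6.3: 120 + 20 = 140 mCi, against 40 mCi in 3.2.1.
- For scale, assuming that dose is proportional to activity: 0.428 / 20 = 0.0214 rem per mCi, so 120 mCi gives 120 × 0.0214 = 2.568 rem. With Visit 3 and two CTs: 140 × 0.0214 + 2 × 0.625 = 4.246 rem, about twice the stated maximum.

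**Reproducing 3.2.1** (total = injections × 0.428 + CTs × 0.625)
- 2 × 0.428 + 2 × 0.625 = 0.856 + 1.250 = 2.106 rem. This matches exactly and contains nothing for DXA.

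**Trying to reproduce 6.2.3**
- Three scans: 3 × 0.428 + 3 × 0.625 = 1.284 + 1.875 = 3.159 rem before DXA.
- Gap: 3.159 − 2.307 = 0.852 rem; 3.159 / 2.307 = 1.37, so 37% above the stated total. DXA can only widen the gap.
- To fit three scans into 2.307 rem at 0.428 rem per injection, each CT could be at most (2.307 − 1.284) / 3 = 0.341 rem, against 0.625 rem in 3.2.1.
- Two scans plus DXA: 2.307 − 2.106 = 0.201 rem left for DXA. By the one-tenth ratio a chest X-ray would then be 2.01 rem, more than three times one of the study CTs (0.625 rem). That reading is not credible if the whole remainder is DXA.
- Among all combinations of 0 to 4 injections and 0 to 4 CTs, only 1 + 3 (2.303 rem) and 4 + 1 (2.337 rem) come within 0.03 rem of 2.307. Neither is a schedule the protocol describes.
- The 7.69 years equals 2.307 / 0.300, so 2.307 was carried into a further calculation. The background printed beside it, 0.3300 mrem, fits neither the unit nor that quotient.

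**Effect on the exclusion.** Two totals classify a person differently only when past-year exposure falls in a band as wide as their difference.
- 2.307 against 2.106: 0.201 rem wide.
- 3.159 against 2.106: 1.053 rem wide.

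The Radiation paragraph refers to FDA limits without a value. Taking 5 rem as an assumption, the bands run from 5 − 2.307 = 2.693 to 5 − 2.106 = 2.894 rem, and from 5 − 3.159 = 1.841 to 2.894 rem.

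**Repeat attempts.** If each of the two scans could be repeated once with a new injection and CT, the total would be 4 × 1.053 = 4.212 rem before DXA.

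**The case against.** The document largely resolves the 120 mCi figure itself. The synopsis, every Visit 3 description, the cap and total in 3.2.1 and the text of 6.2.3 all use 20 mCi. The synopsis describes the procedure as fully as 5.1 and 6.3, so the slip is in two of three descriptions. Tracer preparation follows committee-approved procedures (6.1.1), and nobody is scanned before radiation committee approval (3.2.1). All of this stands. It makes harm unlikely, and nothing suggests that 120 mCi was ever given. It does not make the procedure text right.

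On the totals, 6.2.3 gives no unit doses of its own, so the mismatch depends on carrying over those in 3.2.1. Section 3.2.1 also mentions transmission scans without a separate dose and calls the CTs both whole-body and head scans, so the 0.201 rem remainder need not be all DXA. These points are fair: they leave the origin of 2.307 rem unknown and make the chest X-ray comparison only indicative. They do not reconcile the totals. The protocol offers no other unit doses, and any further source would only add to the three-scan sum.

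On the count, paying for two completed sessions (6.5.7) does not limit injections, and the two-attempt rule could explain a third. The conflict still remains, because 3.2.1 states two injections as a maximum.

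The effect on the exclusion is also small: the two printed totals differ by 0.201 rem, and the documents give no data on how many candidates have prior exposure.

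**Conclusion.** Both parts hold. The activity in 5.1 and 6.3 is wrong by a factor of six against the protocol's own cap. It is very probably a typing error, but in a safety figure that must be corrected. The 6.2.3 total is not what three scans give at the protocol's unit doses: it falls short by at least 0.852 rem. The protocol also states no single maximum scan count.

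At 20 mCi per injection the claim of staying below 5 rem survives for two scans (2.106 rem) and three (3.159 rem). Both figures leave out DXA, for which no value is given, and assume that the unit doses in 3.2.1 apply throughout. The 4.246 rem figure for the printed activities also assumes proportional scaling. No endpoint, estimate or power calculation is affected.

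**What to change.** 1. Change about 120 mCi to about 20 mCi in 5.1 and 6.3, and state the dose in 6.1.2.
2. Set one maximum number of injections and CTs per person, and say whether a repeat under the two-attempt rule involves a new injection and counts towards it.
3. Give DXA a value in rem, and say whether the CT unit dose is for a whole-body or a head scan and whether the 0.428 rem includes transmission scans.
4. Recompute one total and use it in 3.2.1, 6.2.3 and the prior-exposure exclusion, with the yearly limit stated as a number. At the current unit doses it is 2.106 rem plus DXA for two scans, 3.159 rem plus DXA for three, or 4.212 rem plus DXA if both scans may be repeated in full.
5. Correct the background figure in 6.2.3 and recompute the years of background from the new total.

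The cost is a text amendment and a re-check by the radiation committee, with no design change. If two scans is the ceiling, the 3.2.1 total rises only by DXA. If more are allowed, the disclosed exposure rises and the exclusion becomes stricter for people with prior research exposure; the documents do not show how many that would be.

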6.3.1 Study Schedule

HIC 2000030749

Visit 1: Screening Visit
 
 -Review of Consent Form -Physical and Medical history review - Pregnancy Test (females) -EKG -Blood Work -OGTT -Body Composition 
 -Tanita Scale -DXA Scan 	
Visit 2: Whole body PET/CT
 
Imaging
 
Fasting Visit
 
 - Urine Pregnancy Test (females) - Urine Drug Screen - [¹¹C]MRB - Low dose CT scan and PET scan - Norepinephrine levels (serum) 	
Visit 4: SNSA Visit – Fasting
 
 - BP, HR, PI, HR variability - EKG - MSNA
	
Visit 3: Whole body PET/CT
 
Imaging Mixed Meal Test Visit
 
 - [¹¹C]MRB - Urine Pregnancy Test (females) - Urine Drug Screen - Ingestion of mixed meal - Measurement of Energy Intake - Low dose CT scan and PET scan - Norepinephrine levels (serum) 	
Visit 5: SNSA Visit - Mixed Meal
 
Test
 
 - Ingestion of mixed meal BP, HR, PI, HR variability - EKG - MSNA

Abbreviations: BP=blood pressure, EKG=electrocardiogram, HR=heart rate, MSNA=Muscle sympathetic nerve activity, SNSA=Sympathetic Nervous System Activity

6.3.2 Informed Consent

All subjects are consented by one of the study investigators or research staff, as part of determining their study eligibility. The purpose, nature, and potential risks and benefits of the study will be explained to each potential subject in detail during the screening interview.

Prior to initiating the study, one of the study investigators or research staff will explain the planned study interventions, and each subject will be asked to read and sign a consent form approved by the Yale School of Medicine Human Investigation Committee (HIC).

All potential subjects are given ample time to ask questions and only after this are they asked to provide informed consent in the research study. Subjects are given a copy of the signed consent for their personal records.

6.3.3 Screening

Research team members will contact interested potential participants to assess eligibility and provide the participant with additional information about the study, including the study procedures, purpose and potential complications. The brief screen via email or phone will ask for the following information to confirm study eligibility:

- Name
- Age/Date of Birth

HIC 2000030749

- Place of Birth
- Phone Number/Email
- Address
- Marital Status
- Race/Ethnicity
- Height/Weight
- Medical/Surgical History
- Medications
- Drug/Alcohol Use

In order to determine the potential participant's eligibility and avoid unnecessary screening and traveling efforts, it is necessary to collect this information prior to having the subject arrive for an in-person screening visit. This information will be protected according to HIPAA policies and will be destroyed if the individual is determined to not be eligible for the study during this correspondence, or is otherwise not interested in participating in the study, unless the subject consents for his/her screening information to be stored for future studies that he/she may be eligible for.

During the in-person screening visit, the participant will arrive to the Yale New Haven Hospital (YNHH) Research Unit (HRU). The study nurse will collect vital signs, EKG, and the Principal Investigator will review the participant's medical history and perform a physical exam. Fasting blood will be collected for HbA1C, creatinine, liver enzymes (ALT, AST), TSH, hematocrit, and lipid panel. A urine pregnancy test will be administered to females of child bearing potential.

Oral glucose tolerance test (OGTT) will be administered as follows: Following a 10-hour overnight fast, a nurse will insert an intravenous (IV) catheter. Subsequently, subjects will ingest 7.5 oz of Glucola, which contains 75 g of dextrose in orange flavored water. Blood samples will be taken at -15, 0, 10, 20, 30, 60, 90 and 120 minutes (after glucola ingestion) for the measurement of plasma glucose, insulin, and C-peptide concentrations, and calculation of measurements of insulin sensitivity index (Matsuda Index).

Body Composition, Percent Body Fat & Percent Body Water: will be assessed using bioelectrical impedance analysis Tanita® scale (FDA cleared); which is a special multi frequency segmental body composition analyzer that delivers a very mild electrical current that allows measurement of fat mass, percent body fat, fat free mass, total body water, and percent body water. This test will be performed at screening visit. For better accuracy, measurement of percent fat and percent body water will be obtained with whole body Dual X-Ray Absorptiometry (DXA) scan (Hologic®) (located in the HRU) on screening-OGTT visit. The scanner arm will move over the participant's body from feet to head. The machine uses a small amount of radiation (one tenth of the amount of radiation from a chest x-ray) to measure body fat, muscle and bone density.

6.3.4 Enrollment

HIC 2000030749

Research team members will enroll subjects who have been consented and screened during the in-person screening visit to ensure they meet eligibility criteria.

Recruitment Procedures:

Subjects will be recruited through flyers, by word of mouth, and through YCCI email blasts and JDAT.

a. Messaging to Study Participants through JDAT:

The following wording will be used for all applicable recruitment methods:

"You are receiving this [notification, email, letter, phone call] because you may qualify for and be interested in a research study conducted by Yale University investigators looking at whether obesity is associated with increased activity of the sympathetic nervous system.

For JDAT queries only: The Yale New Haven Health electronic health record system has searched medical conditions to find people who may be good matches for research studies. No one has looked at your record and no information has been shared with any research doctor or research team member. Just because you received this message does not mean that you are in a research study or that you have to decide to be in this or any study.

To opt-out of research, including opting out of receiving future messages about research studies, please email [contact] or call [name] and select option #3.

Title of study: Sympathetic Activation in Obesity

Principal Investigator: [name], MD, PhD

Study Coordinator: [name]

[contact]

Description of Study:

The primary objective of this study is to determine whether sympathetic nervous system (SNS) activity in white adipose tissue (WAT) and brown adipose tissue (BAT), skeletal muscle and brain is altered in individuals with obesity in comparison to individuals with normal weight. Simultaneous multi-organ SNS activation will be obtained with a radiotracer for norepinephrine transporter (NET) for whole-body Positron Emission Tomography (PET) imaging and microneurography (peroneal muscle SNS activity).

Confidentiality and Privacy: Any personal health, financial data, and other information gathered in the study will remain confidential and will be stored on a password-protected computer, only accessed by study personnel. When the results of the research are published or discussed, no information will be included that would reveal your identity. We understand that information about you obtained in connection with your health is personal, and we are committed to protecting the privacy of that information. If you would like to learn more about participating in this study, please contact the study coordinator at [contact].

HIC 2000030749

Possible Benefits: The study may have no direct benefit to you, however general advancement of scientific knowledge from this study may include a better understanding of the importance of SNS activation in obesity.

Participation in this study is completely voluntary. You are free to decline to participate, to end participation at any time for any reason, or to refuse to answer any individual question at any time. Refusing to participate will involve no penalty or loss of benefits to which you are otherwise entitled (such as your health care outside the study, the payment for your health care, and your health care benefits).

Questions: If you have any further questions about this study, you may contact the investigator, [name] [name], at [contact]. If you would like to talk with someone other than the researchers to discuss problems, concerns, and questions you may have concerning this research, or to discuss your rights as a research subject, you may contact the Yale Human Investigation Committee at [contact]."

b. Describe how potential subjects are contacted. The subjects will be asked to call us at our main recruitment number or email if they are interested in participating in the research study. Subjects will be contacted back for a confidential phone screening which leads to an in-person screening if eligible.

c. Who is recruiting potential subjects? The PI, in collaboration with study investigators and trained research assistants, is responsible for subject recruitment.

